3. GENERAL INFORMATION

Objective	
To compare test duration and the agreement of summary metrics between the TEMPO, Virtual Eye ELITE, and HFA perimeters.
 
The hypothesis is that the total time to complete visual field assessment will be shorter with the TEMPO perimeter compared to the Virtual Eye ELITE and HFA perimeters.

Test Article(s)	TEMPO (Topcon) Virtual Eye ELITE (Virtual Vision) Humphrey Field Analyzer (Zeiss)
Sample size	54 subjects total
Study Population	Adult patients presenting with best-corrected visual outcomes of 20/30 or better.
Number of sites	One
Study Design	Single center, prospective, randomized, comparative study.
Masking	None.
Variables	
Primary:
 
• Total acquisition time (both eyes) between devices. 
Secondary:
 
• Mean deviation (MD)• Pattern standard deviation (PSD)• Foveal threshold (FT)• Patient questionnaire• Optical coherence tomography (OCT) 
Exploratory:
 
• Visual field index (VFI)• Set up time• False positives, false negatives
Duration / Follow-up	1 Visit

The study will be registered with clinicaltrials.gov.

The study will be conducted in compliance with the protocol, GCP and applicable regulatory requirements

5. INTRODUCTION

Standard automated perimetry (SAP) is the gold standard in diagnosing and managing glaucoma. Two of the most widely used perimeters are the Humphrey Field Analyzer (HFA; Carl Zeiss Meditec) and the Octopus perimeter (Haag-Streit). However, measurements with these 2 devices can be burdensome on patients and time consuming for both clinicians and patients. One reason for this is that eyes are typically tested separately.

Recent alternatives to HFA and Octopus have been developed that offer testing in a small form factor without a large projection bowl. This includes the Virtual Eye ELITE (Virtual Vision) and the Tempo (Topcon).^{1,2} However, there is minimal data to date comparing these 2 devices to HFA.

6. OBJECTIVE(S)

To compare test duration and the agreement of summary metrics between the TEMPO, Virtual Eye ELITE, and HFA perimeters.

7. SUBJECTS

7.1. Subject Population

Eligible test subjects will be adult patients presenting with best-corrected visual acuity of 20/30 or better.

A total of 54 subjects at one site will be enrolled. Subjects must meet the inclusion criteria. Prior to enrollment, subjects will be provided information on the study and asked to sign a patient information and consent form to participate. The patient information and consent form will be approved by an appropriate ethics committee.

7.2. Inclusion Criteria

Subjects are eligible for the study if they meet the following criteria:

- Adult patients with best-corrected visual outcomes of 20/30 or better.

7.3. Exclusion Criteria

If any of the following exclusion criteria are applicable to the subject or either eye, the subject should not be enrolled in the study.

- Unable to tolerate ophthalmic imaging
- Any ocular or systemic conditions, that could affect VF test results, such as age-related macular degeneration, peripheral retinal disease, or severe glaucoma.

The principal investigator reserves the right to declare a patient ineligible or non-evaluable based on medical evidence that indicates they are unsuitable for the trial.

8. STUDY DESIGN

8.1. Study Design

This study is a single center, prospective, randomized, comparative study of visual field assessments between the TEMPO, Virtual Eye ELITE, and HFA perimeters. Subjects will be assessed at 1 visit. Clinical evaluations will include MD, PSD, FT, VFI, OCT, and a questionnaire.

The primary outcome measure will be the total bilateral acquisition time (both eyes) between the devices.

Secondary outcome measures are as follows:

- Mean deviation (MD)
- Pattern standard deviation (PSD)
- Foveal threshold (FT)
- Patient questionnaire
- Optical coherence tomography (OCT)

Exploratory outcome measures are as follows:

- Visual field index (VFI)
- Set up time (time from instructions to acquisition start)
- False positives, false negatives

8.2. Methods Used to Minimize Bias

Patient selection will be based on the patient's interest and the surgeon's opinion as to whether they are a suitable candidate. Subjects will be randomized to perimeter order.

The measurement of visual fields will be conducted in a systematic fashion to minimize bias.

All data collection will be completed through provided Case Report Forms (CRFs) or computer files generated by automated test equipment. All site personnel involved in the study will be trained in regard to conducting study-specific procedures.

8.3. Method of Assigning Subjects to Treatment Arms

Subjects will receive visual field testing with TEMPO, Virtual Eye ELITE, and HFA perimeters in a randomized order using the method of randomly permuted blocks.

9. STUDY PROCEDURE

9.1. *Informed Consent / Subject enrollment*

No subject will be enrolled into the study who does not meet the inclusion/exclusion criteria and does not sign the current approved informed consent document. Informed consent will be obtained prior to collecting any data for the study. The original signed documents will be maintained by the investigator as a permanent part of the subject's medical records. A signed copy will be provided to the subject.

9.2. *Visits and Examinations*

Subjects will participate in one study visit. The visit schedule, complete with window and associated CRF forms, are displayed in Table 9.2-1. Details of each study visit, including testing to be conducted, are provided below.

Table 9.2-1. Visit Schedule

Visit Number	Visit Window	CRF Number
1	Day 0	1

9.2.1. Visit 1

At Visit 1, subjects will be consented, qualified for the study (compared with inclusion/exclusion criteria), and assigned a study ID/subject number. Subject numbers will be assigned sequentially at each site in the order of enrollment.

A medical history will be taken and exams will include the tests described below:

- Total bilateral acquisition time (both eyes) between the devices
- Mean deviation (MD)
- Pattern standard deviation (PSD)
- Foveal threshold (FT)
- Visual field index (VFI)
- Patient questionnaire
- Optical coherence tomography (OCT)
- Set up time (time from instructions to acquisition start)
- False positives, false negatives

In addition, all site-specific, routine, usual standard of care measures should be undertaken.

Measurements should be made as described in section 9.3 below.

9.3. Study Methods and Measurements

All routine testing and basic eye examinations should be carried out at each study visit. Abnormalities should be recorded in the CRF “Comment” section. Specific study examination procedures are outlined below.

9.3.1. Visual Field Testing

Conduct visual field testing using the TEMPO (24-2 AIZE-Rapid), Virtual Eye ELITE (24-2 SITA-Fast), and HFA (24-2 SITA-Fast) perimeters with test using normal protocol testing per usual clinical standards. Record the total set up time and total bilateral acquisition time (both eyes). Give patients a 5-minute rest period in between devices.

9.3.2. Optical Coherence Tomography (OCT)

Acquire OCT scans using the Spectralis (Heidelberg) device.

9.4. Unscheduled Visits

Unscheduled exams may be conducted at the discretion of the Investigator with all relevant information from the exam recorded in the source documents and on the Unscheduled Visit pages within the CRF booklet.

9.5. Discontinued Subjects

Discontinued subjects are those who do not have an exit visit. Subjects may be discontinued from the study at any time if, in the opinion of the investigator, their continued participation in the study poses a risk to their health. The reasons for discontinuation include:

- a. Adverse event;
- b. Lost to follow-up;
- c. Subject decision unrelated to an adverse event;
- d. Protocol violation;
- e. Treatment failure;
- f. Other.

To ensure the safety of all subjects who discontinue prior to the final visit, investigators should assess each subject and, if necessary, advise them of any therapies and/or medical procedures that might be needed to maintain their health. Any changes in medical health and/or use of concomitant medications should also be captured.

10. ANALYSIS PLAN

10.1. Analysis Data Sets

All subjects who are enrolled in the study will be evaluated for safety. Efficacy analyses will be performed based on data from those eyes where the visit was completed.

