10.2.1. Within-treatment Changes

For variables measured on a continuous scale, these summaries will include the sample size, as well as the mean, standard deviation, median, minimum, and maximum. For variables measured on a categorical scale, summaries will provide the number and percentage of eyes in each category. These summaries will be provided for all eyes completing the study.

Comparisons between devices will be done using linear mixed effect models that are adjusted for perimeter order and for multiple measurements with the same patient.

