11. SAMPLE SIZE JUSTIFICATION

Assuming an effect size of 0.5, α 0.05, and power 90%, we estimate the study will require 46 subjects. To account for 15% dropout, the sample size will be increased to 54.

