18.2. Patient Discontinuation

Each study patient may voluntarily discontinue the study at any time they choose. Study patients who cannot complete the study for administrative reasons (e.g., non-compliance, failure to meet visit schedule, etc.) will be discontinued from the study. Study patients discontinued during the enrollment phase of the study will be replaced.

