18.3. Patient Termination

A study patient will be terminated if the study patient develops any severe adverse event that may be related to the study. A study patient will receive appropriate treatment at the discretion of the investigator. Notification of termination will be clearly documented. These study patients are considered to have completed the study and will not be replaced.

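### Efficacy is limited to completed visits, so patients who stop part-way can be dropped along with usable device times, and the loss may be related to the time difference being tested

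*Combined protocol and SAP*

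**What the plan says.** Section 10.1 sets two populations. For safety: "All subjects who are enrolled in the study will be evaluated for safety". For efficacy: "Efficacy analyses will be performed based on data from those eyes where the visit was completed". Section 10.2.1 applies a similar limit to the descriptive tables: "These summaries will be provided for all eyes completing the study". The same section plans device comparisons by linear mixed models that adjust for perimeter order and for repeated measurements on a patient.

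The primary outcome (Section 8.1) is total acquisition time for both eyes. Each subject is tested on all three perimeters at a single visit (Sections 8.3, 9.2 and 9.3.1), and the General Information table gives masking as none. Section 11 sets 46 subjects and then adds an allowance: "To account for 15% dropout, the sample size will be increased to 54".

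Three other provisions affect who is analysed:
- Section 7.3: "The principal investigator reserves the right to declare a patient ineligible or non-evaluable based on medical evidence", where that evidence shows the patient to be unsuitable for the trial. No time limit is given.
- Section 18.2: "Study patients discontinued during the enrollment phase of the study will be replaced".
- Section 18.3, on patients terminated for a severe, possibly related adverse event: "These study patients are considered to have completed the study and will not be replaced".

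The plan does not define visit completion by device. It has no rule for an unfinished test, no tabulation of non-completion by device, and no sensitivity analysis for missing data.

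**The concern.** The introduction justifies the study by how burdensome and slow perimetry can be. Some patients who stop during the visit may do so for reasons linked to those properties. If their between-device time differences are unlike those of patients who finish, an analysis of completed visits estimates the difference in a selected group.

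The rule also discards information without need. A patient who finishes two perimeters and stops during the third has a valid paired comparison of the first two. A mixed model can use that pair; Section 10.1 can remove it.

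Finally, failure to finish a device is itself a relevant finding in a study of test burden, and the plan has nowhere to report it.

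**Working it through.** **1. The plan's own figures.** Inputs from Section 11: effect size 0.5, alpha 0.05, power 90%, 46 subjects, 15% dropout, 54 enrolled. Section 11 does not name the test or say whether it is two-sided. A paired two-sided comparison fits best:
- Normal approximation: (1.960 + 1.282)² / 0.5² = 42.03, so 43.
- Noncentral t: 44.
- Wilcoxon signed-rank, by asymptotic relative efficiency: 44 / 0.955 = 46.1.
- Dropout: 46 / 0.85 = 54.1, and 54 × 0.85 = 45.9.

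The 46 and 54 are therefore reproduced to within a subject or two. The plan allows for about 54 × 0.15 = 8 losses in a one-visit study.

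**2. Shift in the completer mean.** Let D be a patient's between-device time difference in SD units, and q the proportion lost. The documents give no relation between loss and D, so it is assumed here. If the most extreme fraction q on one side of D is lost, the mean among completers moves by φ(z) / (1 − q), with z the (1 − q) normal quantile. If loss instead follows a latent normal variable with correlation ρ to D, the shift is ρ times that. At q = 0.15, z = 1.036 and φ(1.036) / 0.85 = 0.274. With ρ = 0.5 the shift is 0.5 × 0.274 = 0.137.

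| Loss q | Unrelated to D | ρ = 0.5 | Most extreme q lost |
|---|---|---|---|
| 5% | 0 | 0.05 | 0.11 |
| 10% | 0 | 0.10 | 0.20 |
| 15% | 0 | 0.14 | 0.27 |

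Against the planned 0.5 at 15% loss, ρ = 0.5 gives 0.36 or 0.64, and the extreme case gives 0.23 or 0.77, depending on which side is lost.

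**3. Cross-check with a different model.** Suppose non-completers differ by m SD in D from the all-enrolled mean. Completers are then biased by q·m / (1 − q). With q = 0.15 and m = 1 this is 0.15 / 0.85 = 0.18 SD. If the all-enrolled difference is zero, a two-sided test then rejects about 22% of the time with 46 completers, or 25% if losses are replaced up to 54. At q = 0.05 and m = 1 the bias is 0.05 SD and rejection is about 7%. At m = 0 there is no bias. Here too, m is an assumption.

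**4. Who counts as completed.** Section 9.5 treats as discontinued those with no exit visit. Section 18.1 treats completion as finishing the final visit. Section 18.3 counts terminated patients as completed even if testing stopped early. Section 10.1 defines the set by eyes, whereas the primary outcome needs both eyes on a device. From these passages an analyst cannot tell whether a patient who stopped early is in the primary analysis.

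**The case against.** The strongest reply is that the text is milder than it may look, and several inferences go further than it allows.

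- A reader might infer that failing one device removes the patient. No section says so. Under Section 18.1 a patient could abandon one perimeter, finish the visit, and have the other two times enter the mixed model. What stands is that the plan does not define this, and that a patient who leaves before the visit ends can lose finished results.
- A reader might infer that the 15% consists of patients who could not tolerate testing. Section 11 gives no cause, Section 9.5 lists several other reasons, and Section 7.3 already excludes those who cannot tolerate imaging.
- A reader might infer that the rule favours the device that patients fail. Dropping a patient removes all three devices' data, so a patient who is slow on every device changes the paired difference little. Bias requires non-completers to have different between-device differences, which the documents do not show.
- A reader might infer free investigator discretion and general replacement. The non-evaluable clause is tied to medical evidence of unsuitability, replacement is confined to the enrollment phase, and Section 18.3 terminations are not replaced. What remains is that neither provision requires reporting and that the first has no time limit in an unmasked study.

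These replies limit the claim about size and direction. They do not supply a reason for restricting the primary analysis to completed visits.

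**Conclusion.** The concern holds in a limited form. The completed-visit restriction is explicit, can discard valid device times that the planned model could use, and may select patients on something related to the primary outcome. At 15% loss the assumed shift runs from 0 to 0.27 SD, with about 0.14 SD at a latent correlation of 0.5, and it may go either way. All the non-zero values rest on assumptions about why patients stop, and on the full 15% being lost; a smaller loss shrinks them. The documents do not support saying that the result will be biased, or that it will be biased towards a particular device. The conflicting definitions of completion need to be reconciled whatever one thinks about bias.

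**What to change.** - **Section 10.1:** define the primary efficacy set as all randomised subjects with at least one valid device result, analysed as randomised, with every available device time in the Section 10.2.1 mixed model. Keep the completed-visit set as a sensitivity analysis.
- **Reporting:** tabulate non-completion by device with the reason. List any patient declared non-evaluable under Section 7.3 or replaced under Section 18.2, with reason and timing.
- **Definitions:** reconcile Sections 9.5, 10.1, 18.1 and 18.3 on who has completed, and state what counts as a valid result on a device, given that the primary outcome needs both eyes.

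The cost is wording, one CRF field for the reason and one sensitivity analysis. Some subjects will contribute fewer than three devices. Using partial data relies on the missing times being predictable from the observed ones and order. It does not remove bias if the abandoned test would have been unusually long, which is why non-completion should be reported alongside.

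Three stronger measures are not needed for this point. Barring any finding of ineligibility after the first perimetry test could keep patients whose excluded disease appears on the same-day OCT, since no test order is stated. Barring replacement altogether is partly a matter of preference. A censored-time analysis would need abandonment times, which Section 9.3.1 does not ask sites to record.

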10.2. Statistical Methodology

A summary of the data will be prepared for all measurement time points.

10.2.1. Within-treatment Changes

For variables measured on a continuous scale, these summaries will include the sample size, as well as the mean, standard deviation, median, minimum, and maximum. For variables measured on a categorical scale, summaries will provide the number and percentage of eyes in each category. These summaries will be provided for all eyes completing the study.

Comparisons between devices will be done using linear mixed effect models that are adjusted for perimeter order and for multiple measurements with the same patient.

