10.3. General Statistical Considerations

The statistical analyses will be performed using R, version 4.4.0 or higher. Any statistical tests of hypotheses will employ a level of significance of $\alpha=0.05$.

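### Agreement of summary metrics is a stated objective, but as specified no planned analysis reports the spread of within-eye differences between devices that agreement depends on

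*Combined protocol and SAP*

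**What the plan says.** The objective in Section 6, repeated in Section 3, has two parts: "To compare test duration and the agreement of summary metrics between the TEMPO, Virtual Eye ELITE, and HFA perimeters". Section 8.1 makes MD, PSD and FT secondary outcomes and VFI exploratory. The one hypothesis in the documents, in Section 3, concerns time: "The hypothesis is that the total time to complete visual field assessment will be shorter with the TEMPO perimeter".

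Section 10 offers two tools:

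- Descriptive summaries in Section 10.2.1. For continuous variables, "these summaries will include the sample size, as well as the mean, standard deviation, median, minimum, and maximum".
- One sentence on inference, also in Section 10.2.1: "Comparisons between devices will be done using linear mixed effect models", with adjustment for the order of the perimeters and for repeated measurements on a patient.

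Section 10.3 adds: "Any statistical tests of hypotheses will employ a level of significance of" 0.05.

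Sections 8 to 11 name no limits of agreement, intraclass or concordance correlation, equivalence margin or acceptable difference. Section 11 sizes the study on a standardised effect: "Assuming an effect size of 0.5, α 0.05, and power 90%, we estimate the study will require 46 subjects". It gives no precision target for agreement.

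**The concern.** Agreement between two perimeters has two components: the average difference (bias), and the spread of the differences from eye to eye. A fixed device effect in a mixed model addresses the first. The second tells a clinician how far one perimeter's MD may lie from another's in the same eye, and no planned output contains it.

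A significance test on the bias is also a poor proxy for agreement. For a given bias, a noisier device gives a larger standard error and so a less significant result. A small bias measured precisely gives a significant one. Two devices that differ widely in individual eyes could therefore show no significant difference, and two that track each other closely could show one.

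Prespecification is at stake too. If agreement statistics are added after the results are seen, the choice of metric, device pairs and handling of the two eyes will be made with the data in view, in a study that Section 3 describes as unmasked.

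**Working it through.** **1. The plan's own sample size.** Inputs from Section 11: effect size 0.5, α 0.05, power 90%, 46 subjects, 15% dropout, 54 enrolled. The test and its sidedness are not stated; I assume a two-sided paired comparison, since every subject is tested on all three devices (Section 8.3).

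- Normal approximation: (1.96 + 1.2816)² / 0.5² = 42.03, so 43.
- Paired t-test (noncentral t): 44. Dividing by the Wilcoxon signed-rank efficiency 3/π gives 46.1.
- Dropout: 46 / 0.85 = 54.1.

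The stated 46 and 54 are consistent with a paired difference test, whose power at n = 46 is 91.3%. That is sizing for a mean difference, not for agreement.

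**2. Whether the planned summaries supply the missing spread.** For devices A and B with SDs s_A and s_B and between-device correlation r:

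SD of differences = √(s_A² + s_B² − 2·r·s_A·s_B)

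The per-device SDs are planned; r is not. If both SDs equal s, the SD of differences is s·√(2(1 − r)). This is 1.00s at r = 0.5 and 0.45s at r = 0.9. The same descriptive table is thus compatible with limits of agreement that differ more than twofold.

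**3. Whether the test tracks agreement.** The documents give no SD of paired differences, so the SDs below are assumptions. Limits of agreement are bias ± 1.96 SD. Each row is 100,000 simulated trials with 46 subjects, one pair each, and a paired t-test at 0.05.

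| True bias (dB) | SD of differences (dB) | 95% limits of agreement (dB) | Non-significant |
|---|---|---|---|
| 0 | 1 | −1.96 to +1.96 | 95% |
| 0 | 2 | −3.92 to +3.92 | 95% |
| 0 | 4 | −7.84 to +7.84 | 95% |
| 0.5 | 0.5 | −0.48 to +1.48 | about 0% |
| 0.5 | 2 | −3.42 to +4.42 | 62% |

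With zero bias, the test result is unchanged while the limits widen fourfold. With a bias of 0.5 dB, the narrower limits go with significance and the wider ones mostly without.

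**4. Allowing for two eyes.** Both eyes are tested (Section 9.3.1), and the model adjusts for repeated measurements. Let ρ be the inter-eye correlation of the differences. The subject-mean difference has SD × √((1 + ρ)/2). For a true bias of 1 dB, SD 3 dB and n = 46, the noncentrality is √46 / (3·√((1 + ρ)/2)):

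| ρ | SD of subject mean (dB) | Noncentrality | Bias missed |
|---|---|---|---|
| 0 | 2.12 | 3.20 | 12% |
| 0.5 | 2.60 | 2.61 | 28% |
| 1 | 3.00 | 2.26 | 40% |

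In the other direction, take an observed bias of 0.3 dB with SD 1 dB. The limits are −1.7 to +2.3 dB, and t = 0.3·√46 / √((1 + ρ)/2). That gives t = 2.88 and p = 0.006 at ρ = 0, and t = 2.03 and p = 0.048 at ρ = 1. The difference is significant throughout.

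**5. Precision available for limits of agreement.** With one eye per subject and n = 46, the SE of a limit is SD × √(1/46 + 1.96²/(2·45)) = 0.254 SD. The 95% interval is 2.014 × 0.254 = ±0.51 SD (±0.47 SD at n = 54). The short form 1.96·√(3/46) gives ±0.50 SD.

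With two eyes, the large-sample SE is SD × √((1 + ρ)/(2·46) + 1.96²(1 + ρ²)/(4·46)). Multiplied by 1.96, this is ±0.35 SD at ρ = 0, ±0.40 SD at ρ = 0.5 and ±0.49 SD at ρ = 1.

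**The case against.** Several points on the other side stand.

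- **The primary endpoint is unaffected.** The only hypothesis and the primary outcome concern test time. A mixed model of means, adjusted for order, suits that. The gap lies in secondary and exploratory metrics. It does not touch randomisation, data collection or safety.
- **A reader might infer that the plan cannot answer the agreement question.** The documents do not support that. The planned model already gives the bias component, and a suitably structured mixed model could yield variance components for limits of agreement. What is missing is any statement that they will be estimated or reported.
- **A reader might infer that a non-significant result will be taken as agreement.** No section says so. Section 10.3 is conditional, no equivalence claim is made for MD, PSD or FT, and Section 10.2.1 does not restrict the output to p-values. The text supports only that such a result could be misread, because a 0.05 test is the one inferential criterion given.
- **The size depends on assumptions.** All the SDs are assumed. The 40% miss rate is the extreme case in which the second eye adds nothing. The documents give no acceptable limit, so they offer no basis for calling any particular limits close or wide.
- **The analysis is recoverable later.** The paired data will exist in any case, so a late decision would cost prespecification rather than information.

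None of this supplies an agreement analysis. The removed pages lie outside Section 10, and nothing in that section appears redacted.

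**Conclusion.** The point holds as a mismatch between one stated objective and its analysis. As specified, Section 10 estimates bias for MD, PSD, FT and VFI but reports nothing on within-eye spread, so the agreement objective is not answered. The conclusion comes from setting Sections 3 and 6 beside Sections 10 and 11, and does not depend on any assumed number.

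The illustrations show how far the planned test can part from agreement. They rest on normal differences, 46 evaluable subjects and assumed SDs. A non-significant result is equally likely (about 95%) across a fourfold range of limits when bias is zero. A 1 dB bias with SD 3 dB goes undetected in 12% to 40% of trials. The primary comparison of acquisition time is not in question.

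**What to change.** In Section 10.2.1, keep the order-adjusted mixed model as the estimate of bias and add the following for MD, PSD, FT and VFI:

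- Mean bias and 95% limits of agreement, with confidence intervals, for TEMPO vs HFA, Virtual Eye ELITE vs HFA, and TEMPO vs Virtual Eye ELITE.
- Variance components that account for two eyes per subject. One way is to model the within-eye differences for each device pair, with perimeter order and a random subject effect, and to take the SD of differences as the square root of the between-subject plus within-subject variance. This lets the spread differ by pair.
- A sentence stating that a non-significant difference is not evidence of agreement.

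In Section 11, add the expected precision of each limit: about ±0.5 SD of the differences with 46 subjects and one eye each, and somewhat better with two eyes depending on inter-eye correlation (±0.35 to ±0.49 SD by the formula above).

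Two additions are optional: acceptable limits for each metric, set by the sponsor before data are seen, and a check for bias that changes with severity.

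The cost is SAP text and a little more analysis. Every subject is already tested on all three devices, so no new data or patients are needed.

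### Sections 10.1 and 10.2.1 use the eye as the analysis unit but name clustering only by patient, so standard errors for device differences in MD, PSD, FT and VFI could be too large or too small

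*Combined protocol and SAP*

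**What the plan says.** The analysis unit is the eye. Section 10.1: "Efficacy analyses will be performed based on data from those eyes where the visit was completed". Section 10.2.1, on the descriptive tables: "These summaries will be provided for all eyes completing the study". No outcome is exempted.

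The design is crossed. Section 8.3: "Subjects will receive visual field testing with TEMPO, Virtual Eye ELITE, and HFA perimeters in a randomized order". Section 9.3.1 has one acquisition time covering both eyes recorded, so both eyes are tested on each device.

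The model is described in one sentence of Section 10.2.1: a linear mixed model "adjusted for perimeter order and for multiple measurements with the same patient". The random effects are not written out. Sections 10.1 to 10.3 do not mention eye within patient or patient-by-device variation, and do not say whether one eye or both enter the models for the field indices.

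The primary outcome is a patient-level quantity. Section 8.1: "The primary outcome measure will be the total bilateral acquisition time (both eyes) between the devices". Section 11 counts in subjects: "Assuming an effect size of 0.5, α 0.05, and power 90%, we estimate the study will require 46 subjects".

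**The concern.** If both eyes are used, each patient contributes a two-by-three table (eyes by devices) for MD, PSD, FT and VFI. Two features of that table matter for a device contrast.

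- Device varies within an eye, so stable differences between a patient's two eyes cancel from the contrast. A model with only a patient effect leaves them in the residual, and the contrast looks less precise than it is.
- If patients differ in how they respond to a device, both eyes of a patient carry the same deviation. They are then not two independent replicates of the device difference. A model with only a patient effect treats them as if they were, and the contrast looks more precise than it is.

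Agreement of summary metrics is part of the objective in Section 6. MD, PSD and FT are secondary outcomes and VFI is exploratory. Confidence intervals and p-values for device differences in these measures depend on a random-effects structure that the plan leaves open.

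A smaller matter is that an eye-based data set does not fit an outcome defined as one total over both eyes.

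**Working it through.** **The plan's own figure.** Section 11 gives 46 evaluable subjects for effect size 0.5, alpha 0.05 and 90% power. Reading this as a two-sided paired comparison (the test is not named), the normal approximation is ((1.96 + 1.2816)/0.5)² = 42.03 and the paired t-test needs 44. Power at 46 is 91.3%. For dropout, 46/0.85 = 54.1 against 54 stated. The figure reproduces closely, is counted in subjects, and is unaffected by this point.

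**Inputs.** From the documents: two eyes, three devices, 46 evaluable patients. Assumed, because the documents give no variance components: eye-within-patient variance V, patient-by-device variance W and residual variance E, equal across devices. The layout is taken as balanced and the order term is left out.

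**Model with a patient effect only.** Within a patient there are 5 degrees of freedom:

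- eyes, 1 df, expected mean square E + 3V
- patient by device, 2 df, E + 2W
- eye by device, 2 df, E

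The model pools them: (E + 3V + 2E + 4W + 2E)/5 = E + 0.6V + 0.8W. With n patients, the variance it reports for a difference between two device means is 2(E + 0.6V + 0.8W)/(2n) = (E + 0.6V + 0.8W)/n.

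**True variance.** 2(W + E/2)/n = (E + 2W)/n.

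**Ratio of model SE to true SE.** r = √[(E + 0.6V + 0.8W)/(E + 2W)]. Type I error at a nominal two-sided 5% is 2[1 − Φ(1.96r)]. With E = 1:

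| V | W | r | Type I error |
|---|---|---|---|
| 0.5 | 0 | √1.3 = 1.14 | 2.5% |
| 1 | 0 | √1.6 = 1.26 | 1.3% |
| 2 | 0 | √2.2 = 1.48 | 0.4% |
| 1 | 0.5 | √(2/2) = 1.00 | 5% |
| 0.25 | 1 | √(1.95/3) = 0.81 | 11% |
| 0 | 1 | √(1.8/3) = 0.77 | 13% |

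Whenever V = 2W the numerator equals the denominator and r = 1. In the first three rows, a comparison with 90% power under the right model has power Φ(3.24/r − 1.96), that is 81%, 73% and 59%.

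Simulation with 46 patients (20,000 runs) agrees: type I error 1.4% at V = 1, W = 0; 0.4% at V = 2, W = 0; 5.1% at V = 1, W = 0.5.

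**Adding eye within patient but not patient-by-device.** The pooled residual is now (2(E + 2W) + 2E)/4 = E + W, so r = √[(E + W)/(E + 2W)]. At W = 0 this is 1. At W = 0.5 it is √(1.5/2) = 0.87 with type I error about 9%, whatever V is. The eye term alone removes the conservative error and leaves the anti-conservative one, so both terms are needed.

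**Primary outcome.** With one record per patient per device and a patient random intercept, simulated type I error is 5.0%. If each bilateral total were entered on two eye rows, V and E would be zero, giving r = √(0.8/2) = 0.63 and type I error of about 21% (simulated 22%).

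**The case against.** The strongest reply is that this is a gap in the description, not an error in a stated model. Adjusting for multiple measurements in the same patient is compatible with a model that also has eye and patient-by-device terms. Even with a patient intercept alone, the standard error is right when V = 2W, and the variance components are unknown. All of this stands. It means the standard errors can be wrong, not that they are.

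A reader might also infer that the primary analysis double counts and carries a false-positive rate of about 21%. The documents do not support that. Section 9.3.1 records one total per device, Section 11 counts subjects, and no section says the total is copied to each eye. Section 10.1 defines a data set; it does not instruct duplication.

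Two further inferences fail as well. The plan does not say that the questionnaire is completed once per device. It also plans no limits of agreement, so no effect on such limits can be claimed.

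What survives the reply is that the patient is the only level the plan names. An analyst who follows the text as written could reasonably fit a patient intercept alone to eye-level data, and for MD, PSD, FT and VFI that model is right only when the two omitted components happen to balance.

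**Conclusion.** The point holds as a conditional one about the eye-level measures. If both eyes enter the models and only a patient effect is fitted, the standard error of a device contrast is about 1.14 to 1.48 times too large for V between 0.5 and 2 times E with no patient-by-device variance. It is about 0.8 of the true value, with type I error of 11 to 13%, when W is about equal to E and V is small. It is correct when V = 2W. The direction cannot be settled from the documents, because every variance value here is an assumption.

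For bilateral acquisition time the existing model is adequate with one record per patient per device. What is needed there is a clarifying sentence, not a correction. The sample size is unaffected.

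**What to change.** In Section 10.2.1, state that when both eyes are analysed, the models for MD, PSD, FT and VFI include random effects for patient, eye within patient and patient-by-device, alongside the fixed effects of device and perimeter order. Apply the same structure to false-positive and false-negative rates if they are analysed by eye. Drop a term only if its variance is estimated as zero. All the components are estimable from two eyes by three devices.

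In Section 10.1, state that bilateral acquisition time, and set-up time if it is recorded as one total per device, are analysed and summarised with one record per patient per device, counting patients and not eyes.

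The cost is a few sentences and one or two extra random-effect terms in R. No new data are needed and the 46/54 does not change. The drawback is that a variance component may be estimated as zero, which the rule for dropping terms covers.
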